PROTOCOL SYNOPSIS

A Phase 2 Randomized, Double-Blind, Placebo-controlled Study to Evaluate the Effects of Two Doses of MEDI6012 on Apolipoprotein B100 Metabolism in Subjects with Stable Atherosclerotic Cardiovascular Disease.

Principal Investigators:

[name]

Co-Investigator(s):

[name] [name]

Version History:

Version 1. 3/2018

Version 2. 5/2018

Version 3, 7/2018

Version 4. 8/2018

Version 5. 9/2018

Version 6. 10/2018

Version 7. 11/2018

Version 8, 7/2019

Study site(s) and number of subjects planned

Columbia University Medical Center

[name]

This is a single site study that will enroll a maximum of 8 subjects.

Study period		Phase of development
Estimated date of first subject enrolled	12/15/2018	Phase 2
Estimated date of last subject completed	11/30/2019	

1

I. Study design

This is a Phase 2, single-center, placebo controlled, double-blind, randomized crossover study to determine the effects of MEDI6012 on the metabolism of apolipoprotein B100 (apoB100) lipoproteins in individuals with stable atherosclerotic cardiovascular disease (ASCVD). Studies will use stable isotope to determine the *in vivo* kinetics of apoB100 in VLDL, IDL, and LDL as well as VLDL TG. The primary outcome will be the percent difference in the fractional clearance rate (FCR) of LDL apoB100 on treatment with MEDI6012 versus on treatment with placebo. FCR is defined as the percent of the circulating pool of LDL apoB100 cleared from the plasma each day. At least 8 subjects will be randomized at Columbia University Medical Center to evaluate the effect of an IV push dosing regimen that includes a loading dose of 300 mg MEDI6012 followed by a 150 mg maintenance dose of MEDI6012 at 48 hours.

Once consented, subjects will undergo a screening period of up to 28±4 days. For subjects requiring a washout of dyslipidemia medication other than a statin or ezetimibe, or supplement, a 56±2day screening period is allowed (with repeat screening safety and lipids labs within 28±4 days of enrollment). Once enrolled and randomized, subjects will be instructed in an AHA heart healthy diet and stay on that diet, with frequent follow-up telephone calls to obtain diet histories and to reinforce the diet over two weeks before inpatient visit. They will then be admitted to the inpatient research unit of the Irving Institute for Clinical and Translational Research. On day 0, they will arrive in the morning and have fasting blood samples. The first dose of either active drug or placebo will be administered by IV push in the morning hours. They will be observed for the next 2 hrs. for immediate IP reactions and then discharged home with guidelines to continue to follow an AHA Heart Healthy Diet. They will return to our center at 12pm the next day (Day 1-post first dose) and be admitted to our unit for 2 nights. At the time of admission, stat safety bloods will be drawn to ensure no adverse effects from first IP administration. They will be provided with lunch and dinner but will be NPO after 8pm. At 1am (or 8 hrs before the stable isotope administrations) (Day 2) they will start liquid feedings (q2hrs) as part of a protocol obtaining a nutritional steady state before the start of stable isotope administration and kinetic studies. The composition of this liquid formula is 57% carbohydrate, 18% fat, and 25% protein. They will receive the 2nd dose of either active drug or placebo on the morning of Day 2 (exactly 48 hrs. from Day 0 administration). One hour after the second dose (Day 2-9am), a preisotope administration blood draw will be obtained (0hr). Immediately after blood draw stable isotopes will be administered to subjects for the study of lipid and lipoprotein kinetics, and 17 timed blood samples (see procedure schedule) will be obtained for the next 24 hr. followed by discharge. Subjects will repeat this same protocol 6-8 weeks later but will receive the alternative treatment. In the period between the first and second studies, subjects will be monitored and re-instructed as needed in the AHA diet. Two nutritional assessments via 24 hr. recalls will ensure that all subjects maintain a constant healthy lifestyle during the washout period between each study. All subjects will have a 'safety' visit 28±4 days after the first study period. A blood sample will be obtained to ensure that the subject's plasma lipid levels are the same as those during the first study. If they differ significantly, intensive diet and lifestyle counseling will be initiated and continued on a bi-weekly basis for the rest of the inter-study period.

Follow up, for safety monitoring, will also be performed 28±4days after the first and second study. ADA samples will be obtained at days 0 of each inpatient study, as well as 28±4days after the end of the study. If ADA present at day 28±4 days after first study subjects will be monitor after 56±4 days and will not continue to the second period (see subject replacement rules) of the study. If ADA present at day 28±4 days after second study period (active drug), an additional sample for ADA will be obtained at approximately day 56±4 days post study. For both periods, if a subject's Day 56±4 immunogenicity sample is confirmed as ADA positive and there is a > 30% decrease in HDL-C and/or presence of a neutralizing antibody, the subject will return to the study site approximately every 3 months thereafter for additional assessments until their immunogenicity sample is no longer ADA positive or their HDL-C has returned to baseline levels or until approximately 12 months after the 2nd dose of treatment was administered, whichever occurs first. Additional follow-up may be done if clinically/medically necessary.

II. Objectives

Primary objective: To compare the effects of two IV doses of MEDI6012 to two IV doses of placebo on the FCR of LDL-apoB100 (pools/day) in patients with stable atherosclerotic cardiovascular disease.

Secondary objective: To compare the effects of two IV doses of MEDI6012 to two doses of placebo on the production rate (PR) of LDL apoB100 (mg/kg/day) in patients with stable atherosclerotic cardiovascular disease.

Columbia University Medical Center

To access the immunogenicity of MEDI6012 via measurement of ADA.

Exploratory Objectives: To assess the effects of IV doses of MEDI6012 on various parameters of lipoprotein metabolism and kinetics in plasma, including:

- 1. Plasma lipid panel parameters, including total cholesterol, high density lipoprotein cholesterol (HDL-C), TG, and calculated LDL cholesterol (LDL-C) (I determined by automated analyzer), free and esterified cholesterol determined by thin layer chromatography. Cholesterol (free and esterified) and triglyceride levels in isolated lipoprotein fractions (VLDL, IDL, LDL, and HDL) determined by automated analyzer.
- 2. ApoB100 concentration (ELISA) in plasma and in VLDL, IDL and LDL.
- 3. FCR of apoB100 in VLDL and IDL.
- 4. PRs of apoB100 in VLDL and IDL.

5. Conversion of VLDL to LDL.

6. Concentration of apoAI and apoAII in plasma and HDL fractions (ELISA).

7. Lipoprotein particle size and number profile via ion mobility.

8. LCAT Mass (concentrations) in serum.

9. Plasma sterol (campesterol, beta sitosterol, lathostherol) measurements by mass spectrometry.

10. CETP mass by ELISA.

11. Plasma concentrations of apoE and apo-CIII (ELISA).

III. TARGET SUBJECT POPULATION

Adult men or women aged 35 through 80 years with a history of documented stable atherosclerotic CVD. Subjects should be on stable statin dose for greater than 8 weeks. Some may also be on ezetimibe for at least 8 weeks. Women will be postmenopausal.

IV. INVESTIGATIONAL PRODUCT, DOSAGE, AND MODE OF ADMINISTRATION

300 mg of MEDI6012 on Day 0 (loading dose), a second dose of 150 mg 48 hours later (Day 2) – both by IV push over 1-2 minutes.

V. Noninvestigational medicinal product(s) Formulations:

2H3-L-leucine in sterile normal saline

L-phenylalanine-13C6 ring in sterile normal saline

1,1,2,3,3-2H₅-glycerol Routes of

administration:

Bolus:

2H3-L-leucine

L-phenylalanine-13C6 ring

1,1,2,3,3-2H₅-glycerol **IV**

infusion:

2H3-L-leucine administered via a constant IV infusion **Dose regimen**:

IV bolus:

2H3-L-leucine (10 μmol/kg)

L-phenylalanine-13C6 ring (29.4 µmol/kg)

 $[1,1,2,3,3-^{2}H_{5}]$ -glycerol (100 µmol/kg) IV

infusion:

2H3-L-leucine at 10 μmol/kg/h for 15 hours

VI. DURATION OF TREATMENT

Subjects will complete a one-day screening visit and one enrolment visit. Once inclusion and exclusion criteria are met, they will be scheduled for their inpatient stay (within 4 weeks/28±4 days of last safety bloods/screening visit). Subjects who require a washout of lipid treatments will have a screening period of 56±2 days. They will have a second screening visit within28±4 of their inpatient visit. There are two periods in this double-blind, randomized crossover study, separated by a 6-8

week wash out between treatments. Thus, subjects will be randomized to receive two doses of placebo or two doses of MEDI6012 at 0 and 48 hours during the first study period and two doses of the other drug during the second study period. Follow up, for safety monitoring, will be performed 28±4 days after the completion of each study period. ADA samples will be obtained at days 0 of inpatient kinetic outcome study and 28±4 days after each study period. If ADA is present at day 28±4days, a second sample will be obtained as soon as possible and if positive, the subject study order will be unblinded and if the subject was on active drug, the study will be stopped, and that subject will have an additional sample for ADA will obtained at day 56±4. Further follow-up for continued presence of ADA is described above on page. A new subject will be enrolled to replace the one with an incomplete study.

VII. STATISTICAL CONSIDERATIONS

Sample Size: This is an exploratory pilot study. We estimate, from prior studies, that administration of MEDI6012, on the background of high potency statin, will reduce LDL apoB (extrapolating from total apoB changes) by 10-15%. If we assume that there will be no change in LDL apoB PR, we can expect a somewhat larger effect size for LDL apoB FCR: about 15-20%. With 8 subjects studied on placebo and then on treatment, there will be statistical significance (p=0.012, two-tailed), by the nonparametric Wilcoxon signed rank test, if all 8 subjects increase their FCRs, regardless of the magnitude and inter-subject variability of the increases. By the parametric paired t-test, there will be statistical significance if the average increase in FCR is equal to or greater than the SD of the change (e.g., >=20% increase when SD=22%, >=15% increase when SD=17%). In our previous studies, the SD of percent change in paired studies has been smaller than the actual percent change. In other words, there will be statistical significance by a paired t-test if the effect size is 1 or greater, which has been the case in our prior studies.

Therefore, we plan to enroll and complete studies on 8 subjects. Drop-outs will be replaced, although we do not, based on a very long and large experience, expect this to occur.

Statistical Analyses: The primary PD endpoint will be the percent change (and 95% confidence limits) in the FCR of LDL apoB100 during administration of MEDI6012 from the FCR of LDL apoB100 during administration of placebo. The significance of this change will be assessed using either a Wilcoxon Signed Rank test. If the intra-individual variability of change is 17% or less, we can also use a paired t-test at the two-sided alpha level of 0.05.

All PD parameters, including concentrations of lipids and apolipoproteins in isolated lipoproteins, additional lipoprotein kinetic parameters, the concentrations of lipids and apolipoproteins in plasma, and the concentrations and sizes of lipoprotein particles will also be summarized as percentage change (and 95% confidence limits) on active drug versus placebo. Paired t-tests will be used to assess differences, but these will all be exploratory analyses. Plots of the mean and individual subject values will also be provided over time for selected parameters.

VIII. Safety

The safety analysis will be based on the review of descriptive statistics (summary tables) and individual data for adverse events (cases) and clinical laboratory tests. Adverse events will be coded using medical dictionary for regulatory activities (MEDRA), and the number of subjects with treatment-emergent adverse events (TEAEs) will be summarized. Potentially clinically significant abnormalities (PCSAs) for clinical laboratory, vital sign, and ECG data and out-of-normal range values for clinical laboratory data will be flagged and summarized in frequency tables. Results of ADA data will be summarized for each timepoint.

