1.2 Rationale for study design and doses

The premise of MEDI6012 clinical development is that the administration of MEDI6012 in patients with acute MI will increase HDL-C and confer cardio protection by upregulating mobilization of cholesterol from tissues, including cholesterol from atherosclerotic plaques in coronary, cerebrovascular, and peripheral arteries. This will result in stabilization of atherosclerotic plaques and a consequent decreased risk for recurrent major adverse CV events. In addition, expected improvements in HDL function may result in the modulation of inflammation and improvements in endothelial function, effects that may contribute to a reduction in major adverse CV events.

Previous studies with MEDI6012 administered at various doses have shown acceptable safety profile and dose-dependent increases in HDL-C, HDL-CE, and CE (see IB). However, in addition to the lipid changes above, levels of LDL-C were increased by 15%, with no changes, or actual decreases in LDL apoB100 levels of about 10-15%. The current proposal aims to define the mechanisms responsible for LDL-C and LDL- apoB changes.

1.2.1 LDC-C increases:

In the case of rhLCAT administration, if LDL cholesterol levels increase when someone receives rhLCAT, there are several possible mechanisms that can be considered, including:

- a. An increase in VLDL-apoB100 secretion (production rate) into the circulation with greater generation of LDL-apoB100 via conversion of VLDL to LDL.
- b. No change in VLDL-apoB secretion but either an increase in conversion of L to LDL (less direct removal of VLDL remnants) or a decrease in the FCR of LDL apoB100.No changes in either the production of LDL-apoB particles or the FCR of LDL-apoB100 but rather an increase in the size and cholesterol ester content of LDL (same number of particles but more cholesterol per particle).

In the first 2 instances, one would expect that the increase in LDL cholesterol would be accompanied by a similar increase in LDL apoB100 levels. In the last instance, one might see no change in apoB100 or, if the efficiency of LDL particles actually increased, a decrease in LDL apoB100 levels. No change or an increase in the efficiency of LDL clearance, as determined by the FCR, with larger more cholesterol ester enriched LDL particle, would translate to greater delivery of cholesterol to the liver per day (increased reverse cholesterol transport).

1.2.2 LDL-ApoB decreases:

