3.3 Exploratory Endpoint

- a. Plasma levels of total cholesterol, HDL-C, TG, calculated LDL cholesterol (LDL-C) and, ApoB100 measured via automatic analyzer in mg/dl.
- b. Cholesterol and triglyceride levels in lipoprotein fractions (VLDL, IDL, LDL and HDL) via automatic analyzer in mg/dl.

[figure not shown]
C. apob100 concentration (via ELISA) in plasma and in VLDL, IDL and LDL isolated fractions (mg/dl).

- d. Free and esterified cholesterol measured at three times points during each study period via TLC.
 - e. Lipoprotein Kinetic Test
 - The FCR of apoB100 in VLDL, IDL (mg/kg/day)
 - The PR apoB100 in VLDL, IDL (pools/day)
 - the conversion of VLDL to LDL
 - f. the concentration of apoAI and apoAII in plasma and HDL fractions (ELISA) in mg/dl.
 - g. Lipoprotein particle size and number profile via ion mobility.
 - h. LCAT Mass (concentrations) in serum.
 - i. Plasma sterol (campesterol, beta sitosterol, lathostherol) measurements by mass spectrometry.
 - j. CETP mass by ELISA.
 - k. Plasma concentration apolipoprotein E and Apolipoprotein CIII via ELISA.

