Then be admitted to the inpatient research unit of the Irving Institute for Clinical and Translational Research. On day 0, they will arrive in the morning hours and have fasting blood samples (see schedule of events Appendix, Table 1). The first dose of placebo/MEDI6012 will be administered by IV push in the morning. They will be observed for the next 1-2 hrs. for immediate IP reactions and then discharged home with guidelines to continue to follow an AHA Heart Healthy Diet (18). They will return to our center at 12pm the next day (Day 1-post first dose) and be admitted to our unit for 2 nights. At the time of admission, stat safety bloods will be drawn to ensure no adverse effects from first IP administration. They will be provided with lunch and dinner but will be NPO after 8pm. At 1am (Day 2- or 8 hrs before the start of stable isotopes) they will start liquid feedings (q2hrs) as part of obtaining a steady state (diet) before the start of the stable isotope administration and kinetic studies. The composition of this liquid formula is 57% carbohydrate, 18% fat, and 25% protein. They will receive the 2nd dose of placebo/MEDI6012 on the morning of Day 2 (exactly 48 hrs. from Day 0 administration). One hour after the 2nd dose, a pre-stable isotope blood draw will be performed (0hr). Immediately after, stable isotopes will be administered to subjects for the study of lipid and lipoprotein kinetics, and 17 timed blood samples will be obtained for the next 24 hr. followed by discharge. Subjects will repeat this same protocol 6-8 weeks later with alternate treatment from first period. In the period between the first and second studies, subjects will be monitored and re-instructed as needed in the AHA diet. We will ensure that all subjects to maintain a constant healthy lifestyle during the washout period between each study.

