4.4 Dose Rationale

PD observations from the single-ascending dose study of MEDI6012 (D5780C00002) and Cohorts 1 and 2 from the second study (D5780C00005) demonstrated that the rate of increase of HDL-C and apoAI are dose dependent. For future studies in ACS and acute MI subjects, maximizing the rate of increase of HDL-C and apoAI following the first and second

dose, may allow a coupling of the antiatherosclerotic effects of enhanced reverse cholesterol transport with other cardioprotective effects of HDL-C and apoAl resulting in multiple benefits for CHD patients (19-22). Therefore, the above dose regimen will be used for this proposal. The loading dose and maintenance doses have been selected based on PK/PD analysis that integrated PK/PD data from the single-ascending dose study of MEDI6012 (D5780C00002) and PD data from study (D5780C00005). Simulations utilizing the RCT PK/PD model were performed based on the estimated PK/PD parameters to select doses in this study that can characterize MEDI6012 PK and the range of PD effects when administering MEDI6012 with loading and maintenance doses administered via IV push (see IB).

In summary, the proposed dose regimen of MEDI6012 is expected to be well tolerated, and the collected PK/PD data will be appropriate to fulfill the objectives of this study. The follow-up duration of 28±4 days after dosing is deemed appropriate to evaluate the reversibility of potential safety findings and to characterize the potential immunogenicity of MEDI6012 when serum concentration (PK mass) has completely cleared and PD biomarkers return to baseline values. Additional follow-up beyond the initial 28±4 days is appropriate in ADA positive subjects with a concomitant decrease in HDL-C or presence of a neutralizing antibody to ensure an ADA does not have a detrimental effect on endogenous LCAT, a theoretic risk of MEDI6012.

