6.2.5. Kinetic Assessment methods

Lipoprotein Kinetics Test

Lipoprotein Kinetics Tests will be conducted while subjects reside in the inpatient research unit for 2 days (2 nights).

Subjects will be admitted to the inpatient research unit of the Irving Institute for Clinical and Translational Research. On day 0, they will arrive by 7:30am and have fasting blood samples. The first dose of placebo or MEDI6012 will be administered by IV push at 8am. They will be observed for the next 1-2 hrs. for immediate IP reactions and then discharged home with guidelines to continue to follow an AHA Heart Healthy Diet. They will return to our center at 12pm the next day (Day 1-post first dose) and be admitted to our unit for 2 nights. At the time of admission, stat safety bloods will be drawn to ensure no adverse effects from first IP administration. They will be provided with lunch and dinner but will be NPO after 8pm. At 1am (Day 2) they will start liquid feedings (q2hrs) as part of obtaining a steady state (diet) before the start of the stable isotope administration and kinetic studies. The composition of this liquid formula is 57% carbohydrate, 18% fat, and 25% protein. They will receive 16 feedings, which will provide 100% of their caloric needs, for 32 hours. The subjects will not consume any other foods, except the formula, during this period. Non-caloric, caffeine-free liquids will be allowed at this time and during the kinetic study.

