VLDL, IDL LDL and HDL will be isolated from the plasma by sequential ultracentrifugation at the study center using standard methods (12) (19). The quantity (in mg/dL) of TG, cholesterol and apoB100 will be measured in VLDL, IDL, and LDL, and TG and cholesterol will be measured in HDL. ApoB in each lipoprotein will be separated from other proteins in each lipoprotein by sodium dodecyl sulfate (SDS) polyacrylamide gel electrophoresis (PAGE). The band for each protein will be cut out of the gel and then hydrolyzed and derivatized (12) (20). Enrichment with 2H3-leucine and 13Cphenylalanine will be determined by the local laboratory using gas chromatography and mass spectrometry (GC/MS). The enrichment of plasma free leucine and phenylalanine will also be similarly determined. Apo B kinetics in VLDL, IDL, and LDL will be analyzed using both 2H3-leucine and 13Cphenylalanine enrichment data. Similar analyses will be performed to examine VLDL-TG kinetics using 2H5- glycerol enrichment data. PR and FCR values for apoB100 and TG will be derived from those values. The clinical research unit will follow its internal validated procedures for specimen collection, processing and storage.

The clinical research unit will follow its internal validated procedures for specimen collection, processing and storage, and these written procedures will be made available for use by local personnel during the study.

Plasma Lipid Panel

Blood samples for plasma lipid panels will be collected in the morning, in fasting condition (at least a 12-hour fast) at visits shown in the study flow chart. Alcohol consumption within 48 hours and intense physical exercise within 24 hours preceding blood sampling will be discouraged. If the subject is not fasting as required at a visit, he/she will be asked to return on the following day for the blood sampling, emphasizing compliance with the fasting requirement and the allowed time window for the visit.

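### Could the Day 28±4 lipid check, which names no reference sample, let drug washout trigger counselling in one sequence only?

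*Combined protocol and SAP*

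**What the plan says.** The synopsis (I. Study design) schedules a visit 28±4 days after the first study period. A sample taken there is meant to show that "plasma lipid levels are the same as those during the first study". The consequence of a mismatch is also stated: "If they differ significantly, intensive diet and lifestyle counseling will be initiated and continued on a bi-weekly basis", continuing until period 2. The synopsis does not say which period 1 sample is the comparator, which lipid is compared, or how large a difference counts.

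Other sections bear on the reading:

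- Section 6.2.5, on Day 0 of each period: "On day 0, they will arrive by 7:30am and have fasting blood samples". The first dose follows at 8am.
- Section 6.2.5, under Plasma Lipid Panel: "Blood samples for plasma lipid panels will be collected in the morning, in fasting condition (at least a 12-hour fast", at the visits listed in the flow chart.
- Section 3.3: "Free and esterified cholesterol measured at three times points during each study period via TLC". Some lipid measures are therefore repeated within a period.
- Section 1.2, on earlier studies at various doses: "levels of LDL-C were increased by 15%, with no changes, or actual decreases in LDL apoB100 levels of about 10-15" per cent.
- Section 4.4 justifies the 28±4 day follow-up as long enough to observe when "PD biomarkers return to baseline values".
- Section 4.2 describes the interval between periods more briefly: "We will ensure that all subjects to maintain a constant healthy lifestyle during the washout period between each study". It mentions neither the lipid check nor the counselling trigger. Section 6.2.5 keeps the Day 28±4 visit.

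**The concern.** The phrase about the first study covers a whole period, and that period holds both pre-dose and on-treatment samples. The drug is expected to move lipids for a short time. If Day 28±4 values were compared with on-treatment values, a subject who had received active drug first could fail the check with an unchanged diet, simply because the drug had cleared. A check meant to detect dietary drift would then partly detect washout, and only in the active-first sequence.

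The counselling would fall between the check and period 2. With period 2 starting 6 to 8 weeks (42 to 56 days) after period 1, that leaves 42 − 32 = 10 to 56 − 24 = 32 days. For active-first subjects it would precede the placebo kinetic study, which is the denominator of the primary endpoint. With 8 subjects and a paired Wilcoxon or t-test, a sequence-dependent co-intervention looks like a route to bias. Starting counselling after a lipid shift could also hint at treatment order in a double-blind study.

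**Working it through.** The plan states no figure for this check, so there is none to reproduce. Two questions matter: how large the washout signal would be under each reading, and which reading the text supports.

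**1. Size of the washout signal.** Inputs are from section 1.2: LDL-C up 15%; LDL apoB100 unchanged or down 10 to 15%. Section 4.4 supplies the return to baseline. The change from on-treatment back to baseline is 1/(1 + drug effect) − 1.

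| Reference | LDL-C, active-first | LDL apoB100, active-first |
|---|---|---|
| On-treatment | 1/1.15 − 1 = −13.0% | 0%; 1/0.90 − 1 = +11.1%; 1/0.85 − 1 = +17.6% |
| Day 0, pre-dose | 0% | 0% |

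The 15% is a general figure from earlier studies. The documents give no lipid time course over Days 1 to 3 for this regimen, so the first row is indicative only.

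**2. Which sample fits the plan's own rule for lipid panels (morning, at least 12 hours fasted).**

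- Day 0: morning, described as fasting, before the first dose. It fits.
- Day 1: drawn at 12pm on admission and described as urgent safety bloods, not as a fasting lipid draw.
- Day 2: nothing by mouth from 8pm, then formula from 1am. The fast lasts 5 hours, short of 12. The 0 hr sample at about 9am is taken after 8 hours of feeding.
- Later kinetic samples: 16 feedings, two-hourly, cover 32 hours, from 1am on Day 2 to 9am on Day 3. The 24-hour sampling from 9am on Day 2 ends at the same time, so every kinetic sample is taken in the fed period.

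Day 0 is the only described draw that is like for like with a fasting Day 28±4 panel. It also follows two weeks on the heart-healthy diet, so it is the natural baseline for detecting dietary drift.

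**3. Is the asymmetry clean on the on-treatment reading?** No. A fed sample (formula 57% carbohydrate) would be compared with a fasting one in both sequences. Calculated LDL-C subtracts TG/5 (section 6.2.5), so it moves with triglycerides. Placebo-first subjects could therefore also fail the check, and a 0% expected difference for them is not established.

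**4. Would a period or sequence term help?** Work on the log scale with treatment effect τ and period effect π, and let counselling add c to the period 2 value of active-first subjects. The active-minus-placebo differences are τ − π − c (active-first) and τ + π (placebo-first). With an assumed equal split of 4 and 4, the plain mean of the differences is τ − c/2. The period-adjusted estimate, the average of the two sequence means, is also τ − c/2. The planned tests are no worse here than a model with those terms. Counselling given to placebo-first subjects would add c to their active period and push the estimate the opposite way.

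**The case for a change.** The best case for a change is that the gap in the text is certain and closing it would cost a few words. On-treatment lipids are measured for the exploratory endpoints, so such values will exist and could be picked up. An inference towards Day 0, however reasonable, is not a written rule. Even with Day 0 as the reference, the analyte and the size of difference stay open, and the synopsis and section 4.2 do not match in detail.

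Most of that stands as description. The reference and threshold are unwritten, and section 4.2 is thinner than the synopsis, although it contradicts nothing: it keeps monitoring and diet re-instruction. The schedule table that might settle which lipid samples are drawn when is not in the supplied text, so its absence cannot count against the plan.

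The harm does not stand. It needs the reading that the fasting rule disfavours. Even then, the feeding difference blurs the contrast between sequences, and the absence of a period or sequence term is not an aggravating factor. An open threshold with a Day 0 reference carries no drug-related asymmetry, since dietary drift can occur in either sequence. All subjects also receive diet reinforcement, two 24-hour recalls and the same formula feeding in both kinetic studies, which limits what extra counselling could add.

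**Conclusion.** No change to the plan follows. The synopsis leaves out the reference sample, the analyte and the size of difference for the Day 28±4 check. This is missing detail that site staff would sensibly fill with the fasting pre-dose Day 0 sample. On that reading the expected drug-related difference is 0% in both sequences, provided that PD markers return to baseline by about Day 28, as section 4.4 expects.

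Only with an on-treatment reference would washout contribute, at about −13% for LDL-C and 0 to +18% for LDL apoB100 in active-first subjects. Those figures rest on section 1.2's results from various doses. Carrying that through to the LDL apoB100 FCR contrast would need the sequence split, the share of subjects counselled and the effect of counselling on FCR. The documents give none of these, so the size and direction of any bias are unknown. Confidence is limited by the absence of the schedule table from the supplied text.

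### The case for 8 subjects uses a condition on the observed result as if it assured significance; at a true effect of 1 SD the paired t-test has 68% power

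*Combined protocol and SAP*

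**What the plan says.** Section VII of the Protocol Synopsis (Sample Size) calls the trial an exploratory pilot and expects an increase of about 15-20% in LDL apoB FCR. It then gives two conditions for significance with 8 subjects.

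- **Wilcoxon signed-rank test:** significance, with two-tailed p = 0.012, if all 8 subjects increase.
- **Paired t-test:** "there will be statistical significance if the average increase in FCR is equal to or greater than the SD of the change", illustrated by ">=20% increase when SD=22%, >=15% increase when SD=17"%.

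On prior experience it says that "the SD of percent change in paired studies has been smaller than the actual percent change". It restates the t-test condition by saying that "there will be statistical significance by a paired t-test if the effect size is 1 or greater", and adds that its prior studies met this. The next paragraph draws the conclusion: "Therefore, we plan to enroll and complete studies on 8 subjects".

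Under Statistical Analyses, the Wilcoxon test is named for the primary endpoint. If the variability of change is 17% or less, "we can also use a paired t-test at the two-sided alpha level of 0.05". The endpoint is to be reported with 95% confidence limits. Neither paragraph states a power or a type II error.

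**The concern.** A condition on the observed mean and SD says where the rejection region lies. It does not say how often a trial of 8 subjects will land there. The text supplies that condition with an expected effect and with experience from earlier studies, and then concludes that 8 subjects are enough. Read that way, a true effect of 1 SD would ensure significance, and it does not.

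The worked examples add a smaller inconsistency. The sentence asks for a mean change at least as large as the SD, yet 20% is below 22% and 15% is below 17%.

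The primary hypothesis (section 1.3.1) is that MEDI6012 increases LDL apoB100 FCR, and the trial is meant to explain the LDL-C and apoB changes seen earlier. A reader told that significance will follow from the expected effect could take a non-significant result as evidence against increased clearance, when the design would often miss an effect of that size.

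**Working it through.** **Inputs.** Section VII gives 8 completed pairs (7 degrees of freedom), two-sided alpha 0.05 for the t-test, worked examples of 20%/SD 22% and 15%/SD 17%, and a claimed effect size of 1 or more. Normally distributed differences are my assumption. The documents give no SD from the prior studies, so a range is shown.

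**1. The plan's t-test condition, for observed values.** The test statistic is t = (mean/SD) × √8, and the critical value is t(0.975, 7) = 2.365. The smallest significant observed ratio is 2.365/√8 = 0.836.

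| Observed mean/SD | t | two-sided p |
|---|---|---|
| 1.00 | 2.828 | 0.025 |
| 20/22 = 0.909 | 2.571 | 0.037 |
| 15/17 = 0.882 | 2.496 | 0.041 |

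An observed ratio of 1 is therefore sufficient. Both examples would also be significant, because they lie above 0.836, although they lie below the sentence's own threshold of 1.

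**2. The same ratios as true effects.** Power comes from the noncentral t distribution with 7 degrees of freedom and noncentrality d√8, where d is the true mean/SD.

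| True effect | d | Paired-t power |
|---|---|---|
| 15%/SD 17% | 0.88 | 57% |
| 20%/SD 22% | 0.91 | 60% |
| 1 SD | 1.00 | 68% |
| 20%/SD 17% | 1.18 | 81% |
| 1.5 SD | 1.50 | 95% |

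Simulation of 200,000 trials agreed for the first three rows. Power of 80% requires d = 1.16, which is 19.7% at SD 17% (1.156 × 17) or 25.4% at SD 22% (1.156 × 22).

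**3. The Wilcoxon argument.** With all 8 differences positive, the exact two-sided p is 2/2⁸ = 0.008. The plan's 0.012 is the normal approximation without continuity correction: z = (36 − 18)/√(8 × 9 × 17/24) = 18/7.141 = 2.52, p = 0.0117.

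The chance that all 8 increase is Φ(d)⁸: 25% at d = 1, 20% at 0.91 and 19% at 0.88. Significance does not need all 8 to increase, so power is higher than this, and it depends on which version of the test is used.

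| d | Exact test (smaller rank sum ≤ 3) | Uncorrected normal approximation (smaller rank sum ≤ 4) |
|---|---|---|
| 0.88 | about 50% | about 58% |
| 0.91 | about 53% | about 61% |
| 1.00 | about 61% | about 68% |

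The approximation admits a rank sum of 4 because its p there is 0.04995; the exact p is 0.055.

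**The case against.** The strongest defence is that no t-test figure in the text is wrong. A mean at least equal to the SD is a true sufficient condition for the observed ratio, and the text does not say that 1 is the critical value. That stands. A reader might infer from the 0.836 threshold that the rule itself is false; it is only looser than it need be. The mismatch with the worked examples is a drafting slip with no numerical consequence.

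Second, the two examples illustrate roughly where significance begins. Power near such a boundary is always a little above one half, so 57-60% should not be read as the trial's planned power. The text expects the SD to be smaller than the change. On that premise 68% is the floor for the paired t-test, and power could be 81%, 95% or more. That is fair, and it is why the full range is shown. It does not rescue the assurance: at a ratio of exactly 1, which the text says is enough, about 32% of trials would miss, and no SD is given to show how far above 1 the ratio should lie.

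Third, the trial is labelled an exploratory pilot and 95% confidence limits are planned. Both soften the consequence, and it would be wrong to say that the plan leaves a reader no reason for caution over a null result. Neither changes what the sample-size sentence claims, and neither says how a non-significant result would be read.

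Two further inferences are not supported. The t-test sentence is not the only argument offered for 8 subjects, since the Wilcoxon argument stands beside it. The documents also do not say which treatments the prior studies tested, so it cannot be held that their effect sizes came from other drugs.

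**Conclusion.** The point holds in limited form. The stated condition is true of the observed result, but it is used to justify 8 subjects as though it applied to the expected effect, and there it gives no assurance. With 8 pairs, two-sided alpha 0.05 and normal differences, a true effect of 1 SD yields paired-t power of 68%. Signed-rank power there is about 61% by the exact test or 68% by the uncorrected approximation that the plan's p-value reflects. The Wilcoxon argument shares the fault, since its condition is met only about 25% of the time at 1 SD.

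The documents do not support the stronger conclusion that the trial is too small. Power depends on an SD that they do not give, and a pilot may be sized on other grounds. What needs correcting is the claim made for 8 subjects, not the number.

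**What to change.** Keep 8 subjects. Delete the sentence saying that a paired t-test will be significant at an effect size of 1 or more, and replace the two significance conditions with text such as:

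> With 8 pairs, an observed mean change of at least 0.84 SD gives two-sided p ≤ 0.05 by paired t-test (14.2% at SD 17%, 18.4% at SD 22%). If the true effect is 1 SD, power is about 68% by paired t-test and 61% by exact signed-rank test. For true effects of 0.88, 0.91, 1.18 and 1.5 SD, paired-t power is 57%, 60%, 81% and 95%. Power of 80% by paired t-test requires a true effect of 1.16 SD.

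State which version of the signed-rank test will be used; if it is the exact test, the p-value when all 8 subjects increase is 0.008, not 0.012.

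Add that a non-significant result will be interpreted from the planned 95% confidence limits, and will count as evidence against the expected 15-20% increase only if the interval excludes it. Declaring every non-significant result inconclusive would go too far, because a narrow interval near zero would be informative.

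The cost is wording only: no added subjects, and no change to tests or endpoints. The downside is that the stated figure becomes less favourable.
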